### Parametric methods

For some (groups of) variables, it will be relevant to use different types of regression models to study the effect of telehealth. Both difference-in-difference models and structural equation models will be applied. The use of structural equation models allows to study how telehealth affects a group of variables simultaneously. For example, it will be examined whether telehealth affects a group of health variables, a group of user satisfaction variables, or a group of resource use variables simultaneously. Where necessary, we will use structural equation models that consider that the outcome variables are binary / categorical and that the data material has so-called multi-level structure, since the material consists of repeated observations of the same individuals within the same municipality, over time.

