## 1.5 Participating municipalities and scope of the trial

The trial of telehealth is conducted at a total of six local centers. The participating centers are situated in the municipalities of Eid, Bodø, Larvik, Oslo (in the districts of Sagene, Grünerløkka, Gamle Oslo, St. Hanshaugen), Ullensaker (in cooperation with Gjerdrum) and Kristiansand. Kristiansand municipality is leading a local center recruiting patients from 30 municipalities in the Agder county.

Eid municipality, as well as a general practitioner office in Kristiansand and one in the Sagene district also participate in the pilot study of multidisciplinary care teams within primary care. The Norwegian Directorate of Health has asked the research consortium to evaluate synergies between the two trials. However, the telehealth trial is not designed to explicitly examine the effect of participating in both studies, as this was not possible within the frames given by the Norwegian Directorate of Health. Instead, synergies will be investigated through interviews.

The local centers carry out the trial in line with the guidelines from the Norwegian Directorate of Health. The centers also undertake to follow the study protocol for the trial. It is the centers' responsibility to recruit participants to the trial.

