## 4. Treatment – telehealth vs. standard clinical care

### 4.1 Telehealth

#### Organization and responsibilities

The Norwegian Directorate of Health has outlined guidelines on how to organize telehealth in clinical practice, yet the participating municipalities may adapt the service according to local needs (within the guidelines). The local centers are responsible for facilitating cooperation between the general practitioner scheme, the follow-up service and the municipalities' other health and care services. The centers are also responsible for equipment, technological solutions and telehealth software. This includes the procurement, logistics, training in the use of equipment and user support. Four different suppliers of technological solutions are involved in the trial, and consequently, technological solutions may vary across the municipalities. In addition, the centers may differ in their target population (with respect to main diagnoses), main recruitment channels, and the design of the service itself. For example, the follow-up service may have different opening hours or different physical location (e.g. at the emergency room or at the home nursing care unit).

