## 9.2 Randomization

Patients who agree to participate in the trial are randomized 1: 1 to the intervention and control group. The treatment allocation is non-blinded in that both providers and patients will know the outcome of the treatment allocation. The actual randomization is carried out by a project employee in the local centers. The project administration stores sealed randomization envelopes in their office. Each sealed envelope contains a sheet marked with either "tiltak" (intervention) or "kontroll" (control), which determines which group the patient is placed in. For each GP in the trial, there is a separate stack of six envelopes: three "intervention" and three "control". Each time a patient on GP's X's list is invited to an information meeting, the project employee takes the top envelope from GP's stack of envelopes. If more than six patients are recruited on the GP's patient list, the project employee will receive a new stack of six envelopes for this GP. Thus, we can ensure that there will be approximately equal distribution of intervention and control patients from each GP. Oslo Economics distributes the stacks of opaque envelopes to the projects.

If a patient is invited to an information meeting and the patient's GP has not previously been involved in the trial, a separate stack of envelopes for this GP should be obtained prior to the meeting so that the patient can be randomized into the trial.

For each information meeting (chapter 8.3), the project employee takes an envelope from the appropriate GP's stack *without opening it*. The envelope is opened together with the patient after the consent form is signed, and the questionnaire is filled out. If the patient does not agree to participate in the trial, the envelope remains sealed. The project employee brings the sealed envelope back to the office and puts it back in the proper stack of envelopes.

 This randomization technique was considered the best practically implementable technique given the practical implementation of the study.

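### Randomisation is stratified by GP, but the analysis section never names the GP; outcomes analysed as follow-up levels would lose some precision

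*Combined protocol and SAP*

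**What the plan says.** On allocation, Section 9.2 says: "For each GP in the trial, there is a separate stack of six envelopes", three for each arm. The stated aim is "approximately equal distribution of intervention and control patients from each GP". The GP is therefore the randomisation stratum, with blocks of six. Section 5.2 plans for about 100 GPs and lets others join; under 9.2 each newcomer gets a separate stack.

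On analysis, Section 9.4 (Parametric methods) says: "Both difference-in-difference models and structural equation models will be applied". The multilevel part is conditional: "Where necessary, we will use structural equation models" that allow for categorical outcomes and for a multilevel structure, "since the material consists of repeated observations of the same individuals within the same municipality, over time". The terms of the difference-in-difference models are not given. Control variables appear, unnamed, only under sensitivity analysis. The GP is not mentioned as a stratum, covariate or level.

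On the form of each outcome, Section 6.1 compares changes in EQ-5D between arms. No change form is stated for the other two primary outcomes, overall satisfaction (6.2) and cost per person (6.3, computed per year from recruitment). Physical functioning, a secondary outcome, is described in 6.1 as a between-group difference in score.

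**The concern.** An analysis should normally reflect the strata used to randomise. Balancing arms within each GP removes GP-to-GP differences from the arm comparison. A model without the GP still counts those differences as residual error, so its standard error is larger than the true sampling variability.

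The GP plausibly matters here. The GP judges eligibility (5.2), helps to write the follow-up plan (4.1), and remains the doctor of patients in both arms.

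Precision is also short. Section 9.1 says that 600 was set without a power calculation, and Table 7 asks for 712 patients to detect a VAS difference of 0.05. Any precision that the stratification has bought should be kept.

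**Working it through.** **Inputs.** VAS SD 0.238 and difference 0.05 (Table 7); 5% level and 80% power (9.1); 600 patients, so 300 per arm; about 100 GPs (5.2), so 600/100 = 6 patients per GP, or one full stack. The GP-level ICC is not in the documents; 0.02 to 0.20 is an assumed range.

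**1. Reproduce the plan's figure.** n per arm = 2(1.960 + 0.842)² × 0.238² / 0.05² = 355.7, so 356 per arm and 712 in total, as Table 7 states. The calculation contains no GP term.

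**2. Effect of omitting the GP from a level analysis.** Let the total variance be σ², with ICC·σ² between GPs and (1 − ICC)σ² within. With three patients per arm in every GP, the GP effects cancel from the difference in means:

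- true variance of the difference = (1 − ICC)σ² × 2/n
- variance reported by a model without GP ≈ σ² × 2/n
- SE ratio = 1/√(1 − ICC)

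Without any GP variance, the standardised effect is 0.05 / (0.238 × √(2/300)) = 0.05/0.01943 = 2.573. Then:

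- power with GP = Φ(2.573/√(1 − ICC) − 1.960)
- power without GP = Φ((2.573 − 1.960)/√(1 − ICC))
- type I error without GP = 2Φ(−1.960/√(1 − ICC))
- n per arm with GP = 355.7 × (1 − ICC), rounded up

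| Assumed ICC | SE too large by | Type I error without GP | Power without GP | Power with GP | n per arm with GP |
|---|---|---|---|---|---|
| 0.02 | 1.0% | 4.8% | 73.2% | 73.9% | 349 |
| 0.05 | 2.6% | 4.4% | 73.5% | 75.2% | 338 |
| 0.10 | 5.4% | 3.9% | 74.1% | 77.4% | 321 |
| 0.20 | 11.8% | 2.8% | 75.3% | 82.0% | 285 |

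The VAS row serves only to show size. It applies to an outcome analysed as a follow-up level, with 0.238 taken as the total SD.

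**3. Change scores.** If a GP's effect is the same at baseline and follow-up, it drops out of each patient's change, and omitting the GP costs nothing. In simulation (600 patients, six municipalities, blocks of six per GP, 1,500 runs per setting), the ratio of model SE to empirical SE for change scores was 0.96 to 1.02. Simulation noise is about 1/√(2 × 1500) = 1.8%, so no systematic excess was seen. GP differences in trend would survive the differencing.

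**4. Incomplete stacks.** For levels at ICC 0.20, the simulated ratio was 1.109 with 100 full stacks, 1.081 with 100 uneven stacks and 1.049 with 200 potential GPs and uneven stacks. At lower ICCs single simulated settings scatter: at ICC 0.10 with full stacks, one set gave 1.007 and another 0.0815/0.0763 = 1.068, on either side of the formula's 1.054. The full-stack figures above therefore rest on the formula.

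**5. Form of the GP term.** With 200 potential GPs, GP fixed effects on a change score raised the SE from about 0.0195 to 0.0210 and cut power from about 72% to about 66%. A random intercept on follow-up levels (outcome SD set to 1) did not show this penalty:

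| Setting | SE without GP | SE with random GP | Rejection under the null, without / with |
|---|---|---|---|
| ICC 0 | 0.0815 | 0.0811 | – |
| ICC 0, 200 uneven GPs | 0.0817 | 0.0814 | – |
| ICC 0.10, full stacks | 0.0815 | 0.0773 | 3.6% / 4.5% |
| ICC 0.20, full stacks | 0.0816 | 0.0730 | 2.7% / 5.1% |
| ICC 0.20, 200 uneven GPs | – | – | 3.8% / 5.5% |

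**The case against.** The strongest reply is that the plan largely analyses changes. EQ-5D is compared as change, difference-in-difference models are planned, and the other primary outcomes have pre-randomisation data: the baseline questionnaire asks about satisfaction, and register data start in 2017. Stable GP differences would then cancel. This stands for EQ-5D, and for any other outcome that is in fact analysed as change. It does not settle satisfaction or cost, because the plan never says which model applies to which outcome.

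The second reply is that the multilevel sentence in 9.4 explains an optional feature of the structural equation models and does not specify the primary analysis. This also stands. A reader might infer that the plan chose municipality in place of GP; the documents support only that the GP is absent by silence.

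A reader might also infer that municipality is the wrong unit because "Kristiansand municipality is leading a local center recruiting patients from 30 municipalities in the Agder county", all served by one follow-up service and one supplier. The documents do not say the latter. The synopsis lists six participating municipalities, so the word in 9.4 may mean the six centers, and Section 4.1 says "Four different suppliers of technological solutions are involved in the trial, and consequently, technological solutions may vary across the municipalities".

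Finally, the size rests on an assumed ICC and is small at modest values: up to about 5% in the standard error, and about 3 points of power, at an ICC of 0.10 or less.

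**Conclusion.** The omission is real: the randomisation stratum appears nowhere in the analysis section. Its consequence is conditional. For outcomes that vary between GPs and are analysed as follow-up levels, standard errors without the GP are conservative, by about 1% to 5% at ICCs of 0.02 to 0.10 and about 12% at 0.20 with full stacks, and by less with incomplete ones. Where GPs differ in trend, some excess also remains in change analyses. With stable GP differences, change and difference-in-difference analyses lose about nothing.

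A reader might infer that all the trial's confidence intervals will be too wide. The planned change comparisons do not support that. Nor is there a risk of false positives from this source, since the error runs the other way. I am confident of the omission and its direction; the size depends on an ICC that the documents do not give. It is worth correcting because the correction is cheap and the sample was not sized for the smaller effects in Table 7.

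**What to change.** In 9.4, state that the between-arm regression models for the primary outcomes include the GP randomisation stack as a random intercept, with repeated measures nested in patient and with center (or municipality) kept as a higher-level term. Specify random rather than fixed GP effects, because fixed effects cost power when stacks are sparse, and say how GPs with a single patient are handled (a random intercept keeps them in the analysis). State for each primary outcome whether it is analysed as a level or a change. The non-parametric tests in 9.4 cannot carry this term, so the sentence should be limited to the regression models.

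Add the GP or stack identifier to the eCRF at randomisation. A reader might assume that it is already collected, but the fields listed in 8.2 do not include it. The General practitioner register in Table 3 gives the patient's GP, but may show a different one after a change of doctor.

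The cost is a sentence or two in the plan, one extra recorded field and a slightly more complex model. No additional patients or visits are needed.

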### Explanation variables and sensitivity analysis

There is considerable variation in the study. This applies to both the variation in the study population and the organization of the service. Sensitivity analyses will be carried out through inclusion of control variables and subsample analyses, but the extent of such analyses is limited by the relatively small sample size.

## 9.5 Analysis of loss-to-follow-up

We expect loss-to-follow-up among the participants in the ITT population, and it is important to document this in order to be able to interpret the results. Patients can drop out either before or after consent is given.

We will register anonymous information about patients who drop out before consent is given. This includes gender, age (in intervals), main diagnosis, recruitment channel, reason for non-participation.

Drop-out that occur after the consent has been obtained will be analyzed to ensure that drop-out does not drive the results. Characteristics of those who drop out will be compared to those who complete the follow-up.

Drop out will also be highlighted through interviews with GPs and other health personnel, as well as with the project administration.

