## 5.6 After the follow-up period

After completing the 18-month follow-up period, the participants can have a new the assessment of eligibility for the use of telehealth if the municipality continues the service. If a patient in the intervention group still receives telehealth, we will continue to record information from the follow-up service unless the patient does not consent to this. We will collect this information until June 30, 2021.

We will obtain registry data information covering all participants in the period 2017-2022. We collect data after the follow-up period to allow potential analyses of longer-term effects.

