## 9.3 Sample for analysis

We will study the following range of patients:

- Intention to treat (ITT) population: this is the sample of randomized patients, regardless of whether they are followed up using telehealth or not
- Per-protocol (PP) population: this is the sub-sample of the ITT population that follows the study protocol during the entire follow-up period (12-18 months)
- Safety population: this is the subset of the ITT population that begins follow-up (uses telehealth), and either completes follow-up or withdraws from the study.

The analysis will mainly be carried out using the ITT population. The reason for this is that loss-to-follow-up is likely to bias the results so that we estimate a greater effect of the use of telehealth than what is estimated by focusing on the PP population. Thus, an analysis of the ITT population is a more conservative estimate.

In addition, we will carry out analyses where we compare the outcome of the intervention group with one or more registry-based control groups. The control groups can be selected based on discretionary assessments and / or by means of statistical methods, e.g. propensity score matching. It will be possible to base the choice of control group on variables such as gender, age, diagnosis and municipality of residence. The results of such an analysis will have to be interpreted with caution but will constitute an interesting supplement to the rest of the analysis.

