### Non-parametric methods

For several variables, both from registers and from the surveys, we will use non-parametric tests such as Wilcoxon signed ranks test or McNemar test. In these tests, each of the collected variables is examined separately, and the null hypothesis is that there is no difference between the intervention and control group. This null hypothesis could be rejected if the individual test's test observer is above critical limit. We will use the conventional significance level of 5% in the statistical analyses. For the analyses of variables where we utilize the randomization of intervention and control group, statistically significant differences between the groups could have interpretation as causal effects.

For parts of the data material, information will only be available for the participants in the intervention group. This applies to information that is directly related to receiving telehealth. In these cases, we will investigate whether there are changes in outcomes over time. The choice of statistical method could be the same as for other analyses. Significant changes will usually be interpreted as significant associations, but care will be taken to interpret any findings as causal effects.

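### The drop-out analysis in section 9.5 cannot show that drop-out leaves the results unaffected, and the plan states no method for missing EQ-5D or satisfaction answers

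*Combined protocol and SAP*

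**What the plan says.** Section 9.5 expects losses: "We expect loss-to-follow-up among the participants in the ITT population". It then sets an aim for drop-out after consent: "Drop-out that occur after the consent has been obtained will be analyzed to ensure that drop-out does not drive the results". The method follows in one sentence: "Characteristics of those who drop out will be compared to those who complete the follow-up". The section adds a qualitative source: "Drop out will also be highlighted through interviews with GPs and other health personnel, as well as with the project administration". It gives no expected drop-out rate and does not mention treatment arm.

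Section 9.3 says "The analysis will mainly be carried out using the ITT population" and gives as the reason that "loss-to-follow-up is likely to bias the results so that we estimate a greater effect of the use of telehealth" than the per-protocol comparison would show. It has no rule for randomised patients whose outcome was never observed.

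For several variables, section 9.4 says "we will use non-parametric tests such as Wilcoxon signed ranks test or McNemar test". It also plans difference-in-difference and structural equation models, multilevel where needed for repeated observations. The sensitivity analyses listed there are control variables and subsamples. Nothing in 9.4 addresses missing values.

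On registers, section 5.6 says "We will obtain registry data information covering all participants in the period 2017-2022". Section 5.7 limits this: data are deleted when consent is withdrawn, and patients who leave but keep their consent are asked whether register data may still be collected.

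**The concern.** Two of the three primary endpoints, EQ-5D and overall satisfaction, come from questionnaires that are posted after baseline in an open trial. Patients learn their allocation when the envelope is opened, and entry requires motivation to use telehealth. It is therefore plausible, though the documents do not show it, that different kinds of patient stop answering in the two arms. That pattern biases a treatment comparison.

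An intention-to-treat label does not help when the outcome is missing. The patient belongs to the population but contributes nothing unless a model or an imputation brings the patient in. If the planned check finds drop-outs and completers alike, a reader will take the stated aim as met, although the estimated effect could still be partly or wholly produced by who answered.

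**Working it through.** **1. The plan's own figure.** Table 7, panel A, uses SD 0.238 for the VAS on a 0-1 scale. With two-sided 5% and 80% power, n per arm = 2 × 2.80² × (0.238/0.05)² ≈ 356, as stated. No allowance for drop-out is included.

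**2. Can a comparison across both arms miss the bias?** Suppose there is no true effect and a fraction d drops out of each arm. Intervention drop-outs lie x SD below their arm mean, and control drop-outs x SD above theirs. Over both arms together, drop-outs and completers then have the same mean. Among completers, the difference between arms is 2 × d × x × SD/(1 − d):

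- d = 20%, x = 0.2: 2 × 0.2 × 0.2 × 0.238/0.8 = 0.024
- d = 20%, x = 0.5: 2 × 0.2 × 0.5 × 0.238/0.8 = 0.060
- d = 30%, x = 0.5: 2 × 0.3 × 0.5 × 0.238/0.7 = 0.102

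Table 7 targets 0.05 to 0.105.

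**3. Size under weak selection.** Assumptions, none of them in the documents: non-response d of 10-40%, and correlation 0.2 between the tendency to respond and the outcome. The shift in one arm is 0.2 × φ(z_d)/(1 − d) × 0.238, where φ is the normal density at the quantile for d. At d = 20% this is 0.2 × 0.350 × 0.238 = 0.0167. Opposite selection in the two arms doubles it. The detectable difference is 2.80 × 0.238 × √(2/n), with n = 300 × (1 − d) responders per arm.

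| Non-response | Bias, one arm | Bias, opposite | Responders per arm | Detectable difference | Opposite/detectable |
|---|---|---|---|---|---|
| 10% | 0.009 | 0.019 | 270 | 0.057 | 32% |
| 20% | 0.017 | 0.033 | 240 | 0.061 | 55% |
| 30% | 0.024 | 0.047 | 210 | 0.065 | 73% |
| 40% | 0.031 | 0.061 | 180 | 0.070 | 87% |

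Equal selection in the same direction in both arms cancels.

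**4. Would the check notice?** Simulation with 300 per arm, 600 runs per setting and no true effect. Drop-out of 10-40% depended on one observed characteristic, in opposite directions by arm (log-odds 0.3 or 0.6 per SD), and that characteristic had correlation 0.3-0.7 with the outcome.

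- A comparison over both arms flagged a difference in about 3-9% of trials, which is near chance. The completer bias was 0.004-0.073.
- A test of whether the drop-out difference varies by arm flagged it in 56-100%.
- Adjusting by arm for that characteristic removed the bias.
- When drop-out depended instead on the unseen outcome (correlation 0.5 with the observed variable), adjustment removed only about a quarter, for example from 0.041 to 0.031. In that case even a by-arm comparison is no assurance.

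**The case against.** The plan has more protection than section 9.5 alone suggests. The questionnaire in Appendix B is backed by reminders by mail and then by phone. Section 5.7 asks patients who leave without withdrawing consent to go on with questionnaires. Section 8.2 records allocation, start and end dates, and why follow-up stopped. This stands, so it would be wrong to call the comparison the only safeguard. But these steps reduce or describe loss; none corrects an estimate for it.

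A reader might infer that section 9.5 pools the arms. The text does not say so; it is silent on arm, and the supportable point is that a by-arm split is not specified.

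A reader might also infer that EQ-5D and satisfaction will be analysed in complete pairs only. Section 9.4 does not support that. The paired tests, which do drop incomplete pairs, are examples for several variables and are not assigned to these endpoints. The planned models on repeated observations could use partial data. What remains is that the plan does not say how they treat missing values.

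Finally, the register data should not be read as a correction in hand. They contain neither EQ-5D nor satisfaction, they are lost when consent is withdrawn, and collection runs to the end of 2022, whereas Table 8 dates the final report to late 2021.

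**Conclusion.** The concern holds in this form: section 9.5 states an aim and a method, and the method cannot meet the aim. The plan also names no handling of missing answers for two primary endpoints. This should be settled before outcomes are analysed.

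The figures show a mechanism and do not forecast the bias in this trial. Under the stated assumptions, the bias runs from about 0.009 (one arm, 10% non-response) to 0.061 (opposite selection, 40%). At 20% loss, opposite selection gives 0.033, about 55% of the detectable 0.061, and selection in one arm gives half of that. The SD of 0.238 belongs to the VAS. It is not the SD of the EQ-5D index or of change, and it says nothing about the four-point satisfaction item. The register-based cost endpoint is not affected by questionnaire non-response, only by loss of consent.

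**What to change.** 1. In section 9.5, report drop-out and questionnaire non-response by arm (rates, timing, reasons and baseline values), and compare drop-outs with completers within each arm. Section 8.2 already provides for recording much of this.
2. In section 9.4, state that the EQ-5D and satisfaction effects are estimated from all randomised patients whose consent stands. Use a mixed model on all survey waves, or multiple imputation by arm from baseline answers, earlier waves and, where consented and available in time, register data.
3. Add a delta-adjusted sensitivity analysis that shifts the imputed values in one arm until the conclusion changes, and report that shift.
4. Reword the aim in section 9.5 so that it promises to assess the influence of drop-out, not to exclude it.

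The cost is additional analysis work and some text; no new data collection is needed. Register data help only for patients who keep their consent, and only as far as they predict the missing answers. That is why the third step is needed as well as the second.
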